### **11.2 Blood Sampling**

Up to 10 mL of venous blood will be drawn during visits 3 and 4 in total. This is less than a tablespoon. The risks of drawing blood include pain, bruising, bleeding, and small chance of infection from the needle sticks. One ~5mL sample will be drawn during visit 1 to determine eligibility.

### **11.3 Percutaneous Vastus Lateralis Muscle Biopsy**

The risks of this procedure include pain, bruising, bleeding, scar formation, and infection. This procedure will be done using aseptic technique by licensed study staff (MD or PA) after injection of local anesthesia (1% plain lidocaine). Approximately 100mg of tissue will be removed from the vastus lateralis muscle (subject's choice of left or right leg).

### **11.3 Study Meals**

The menu for study meals will be presented to subjects during Visit 1 to elicit whether any food allergies or intolerances are present.

### **11.4 DXA Scan**

Subjects will undergo a DXA scan for whole-body composition. The radiation exposure for one DXA scan is approximately equal to ½ of the radiation from a chest x-ray.

### **11.5 Confidentiality**

A potential risk to study subjects is the loss of confidentiality. Measures to protect the confidentiality of study subjects will be implemented as described in the Data Handling and Recordkeeping section above.

## **11.6 Data Safety Monitoring Plan**

- Study staff will ask subjects about the occurrence of adverse events during visits.
- The PI and study physician are responsible for reviewing and evaluating adverse events.
- Adverse events will be recorded in the CRF and on an excel spreadsheet that is submitted to the IRB at required intervals.
- Serious adverse events will be reported to the IRB within 24 hours of their discovery.

---

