## Study Schema

Recruiting will be performed via word of mouth, TRI subject database (ARresearch.org), and the UAMS social media platforms.

Visit 1: informed consent process takes place at the RIOA. Enrolled subjects undergo body composition test and DXA scan (or at Visit 2) using PI's equipment.  
Randomization (1:1:1) occurs.

Visit 2: subjects undergo body composition test and DXA scan if not done at Visit 1.  
Run-in meals are dispensed.

Visit 3: Subjects report fasted to the RIOA to begin a 13-hour visit that entails stable isotope ingestion, blood/urine/saliva sampling and study meal ingestion.

Visit 4: Subjects report fasted to the RIOA the morning after visit 3 to undergo blood, saliva, urine and muscle sampling approximately 24 hours after isotope ingestion.

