**Study Calendar**

Procedure	Visit 1	Visit 2	Visit 3	Visit 4
Informed consent	X			
DXA scan	X 	X		
Body composition testing	X 	X		
Randomization	X			
Pick up run-in meals		X		
24-hour stable isotope procedure			Start	Finish

Or at Visit 2.

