### **4.0 Study Population**

---

Up to 50 subjects of any gender or ethnicity will be enrolled with a target of n=30 for study completion. Subjects' duration of participation is approximately 2 weeks.

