#### **4.4 Subject Compensation**

Subjects will be compensated for participation as shown in the table below. They will be mailed a check to the address they provide through UAMS SAP program. Parking passes will be provided to all subjects for all visits at no cost to subjects.

Visit 1	\$20
Visit 2	\$20
Visit 3	\$360
Visit 4	\$120

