Visit 3: This visit will take place at the UAMS RIOA on the morning after subject completes the 2-day run-in meals. At this visit, subjects will report having fasted for 10 or more hours. This visit is expected to take about 13 hours. During this visit, subjects will be asked to provide blood/urine/saliva samples. They will ingest deuterated water (~3mL per kg body weight) at specific times (total dose divided into 10 aliquots and ingested every hour up to study hour 9:00) and 2g of a stable isotope of alanine (15N-alanine) dissolved in water. Two (group-specific) study meals will be served, one in the morning and one in the afternoon/evening. See **Figure 2** for a timeline. After the second saliva sample has been collected, subjects will go home and return to the study site the following morning having fasted overnight.

Visit 4: This visit will take place at the UAMS RIOA on the morning after visit 3. Subjects will fast overnight between visits 3 and 4. Approximately 24-hours after isotope ingestion, the final biological samples will be collected and the subject offered a snack and beverage. They will then be dismissed.

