## **8.4 Muscle**

At Visit 4, qualified and credentialed study staff (M.D. or PA) will perform a vastus lateralis muscle biopsy of the subject's outer thigh using 1% plain lidocaine for anesthesia. Approximately 100mg of muscle tissue will be obtained using a Bergstrom needle. The tissue will be rinsed with normal saline and flash frozen using liquid nitrogen. The sample will be transferred into a labelled cryo tube and frozen at < -60 degrees C in the PI's lab.

---

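### No staff-initiated adverse event enquiry is scheduled after dismissal from Visit 4, the visit at which the muscle biopsy is done

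*Combined protocol and SAP*

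**What the plan says.** All references are to the combined protocol and SAP.

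- **Finding adverse events.** Section 11.6 states: "Study staff will ask subjects about the occurrence of adverse events during visits". The investigator and study physician evaluate events. These are recorded in the CRF and on a spreadsheet that goes to the IRB at set intervals. Serious events go to the IRB within 24 hours of being discovered.
- **The biopsy.** Section 8.4: "At Visit 4, qualified and credentialed study staff (M.D. or PA) will perform a vastus lateralis muscle biopsy". About 100 mg of tissue is taken with a Bergstrom needle under local anaesthetic.
- **Its risks.** Section 11.3 on the biopsy: "The risks of this procedure include pain, bruising, bleeding, scar formation, and infection".
- **The last visit.** Study Schema: "Visit 4: Subjects report fasted to the RIOA the morning after visit 3 to undergo blood, saliva, urine and muscle sampling". Section 5.0 closes Visit 4 with: "the final biological samples will be collected and the subject offered a snack and beverage. They will then be dismissed".
- **The calendar.** The last row of the Study Calendar is the "24-hour stable isotope procedure", which finishes at Visit 4.
- **Numbers.** Section 4.0: "Up to 50 subjects of any gender or ethnicity will be enrolled with a target of n=30 for study completion".

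**The concern.** The most invasive procedure in the study comes at the end of the schedule, and adverse event enquiry is tied to the visits. Pain, bleeding or early bruising may show while the subject is still on site. An infection introduced at the biopsy would not be expected to show before the subject leaves, and bleeding can also start later. Followed exactly, the plan never asks about either.

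What is at stake is subject safety and the completeness of the harm record. The people responsible for evaluating adverse events cannot evaluate one they have not heard of. The 24-hour rule for serious events runs from discovery, so after Visit 4 it too depends on the subject getting in touch. Section 11.0 says participants gain no direct benefit. The biopsy is done for research alone, which strengthens the case for asking once whether it did harm. A missed minor bruise or sore thigh matters little; a wound infection or later bleed is the reason to act.

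**Working it through.** The plan gives no figure to reproduce on this point. The check is to set the schedule beside the method of enquiry, and then to size the remedy.

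**Step 1: when staff ask.** Section 11.6 places enquiry within visits. It does not say that this is the only method, but the documents describe no other active one.

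**Step 2: what is scheduled, and whether anything follows Visit 4.**

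| Place | Last contact listed |
|---|---|
| Study Schema | Visit 4 |
| Study Calendar | Visit 4, finish of the isotope procedure |
| 4.4 Subject Compensation | Visit 4 |
| 5.0 Study Visits | Visit 4, ending in dismissal |
| 11.6 Data Safety Monitoring Plan | No contact outside visits |

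Payment does not create a later contact, because section 4.4 says: "They will be mailed a check to the address they provide through UAMS SAP program". Figure 2 is not shown, but the text cites it for the Visit 3 timeline and for sample times. Nothing in the text points to it for follow-up after Visit 4. The stated participation of about 2 weeks defines no period after the biopsy.

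**Step 3: where the biopsy falls.** Section 8.4 puts it at Visit 4, which is visit 4 of 4. The subject is on site for the remainder of that visit and is then dismissed.

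**Step 4: count.** Scheduled visits after Visit 4: 4 − 4 = 0. Scheduled calls or messages after Visit 4: 0. Scheduled adverse event enquiries after dismissal: 0 + 0 = 0. Enquiry between the biopsy and dismissal remains possible, since Visit 4 is a visit and nothing fixes the question before the biopsy.

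**Step 5: who is affected.** Section 4.0 gives 30 planned completers and at most 50 enrolled. All 30 completers would have the biopsy. The 50 is a ceiling that would apply only if everyone enrolled reached Visit 4.

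**Step 6: staff time for one follow-up contact.** The documents give no time per call, so 5 minutes per attempt is assumed. Hours = subjects × attempts × 5 / 60.

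| Subjects | Attempts each | Minutes | Hours |
|---|---|---|---|
| 30 | 1 | 150 | 2.5 |
| 30 | 3 | 450 | 7.5 |
| 50 | 1 | 250 | 4.2 |
| 50 | 3 | 750 | 12.5 |

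CRF entry and physician referrals come on top of these hours.

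**The case against.** The strongest reply is that the remaining risk is small and the plan is not silent about it. The biopsy is a single sample, taken aseptically by an MD or PA. Section 4.2 excludes people on prescription blood thinners, those who will not stop aspirin for 7 days before Visit 3, and those with anaemia or abnormal white cell counts. An infected or bleeding wound is something a subject would notice. Any event that is reported would still be recorded and evaluated under section 11.6. All three groups have the same biopsy, so no planned comparison is biased.

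All of that stands, and it limits how serious the point is. It does not close the gap: exclusions and aseptic technique make harm less likely, but they do not find out whether it happened.

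Two stronger readings are tempting, and the documents support neither.

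- A reader might infer that no enquiry at all follows the biopsy. Enquiry takes place during visits, Visit 4 is a visit, and the subject is offered a snack before leaving. Staff may ask in that interval, so the zero applies from dismissal onward.
- A reader might infer that delayed harm reaches the study only if the subject reports it without prompting. Section 12.0 says each participant receives a copy of the signed consent form. That form was not available for review and may say what to watch for and whom to call. This would still be contact started by the subject, but it would be prompted. Section 12.0 also commits the study to institutional policies that cannot be seen here.

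**Conclusion.** The point holds as a gap in active follow-up. The protocol schedules 0 staff-initiated adverse event enquiries after dismissal from Visit 4, for 30 planned completers and at most 50 enrolled. Delayed biopsy harm, chiefly infection or later bleeding, would reach the investigator, study physician and IRB only through a report that the subject starts.

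This rests on the protocol text alone and on reading section 11.6 as a full statement of how events are actively sought. An aftercare call described in unseen site procedures would narrow the gap in practice, but the protocol would still not require it.

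The documents give no complication rate, so no probability of a missed event can be stated. Nor do they support a claim that reported events would go unrecorded or that any efficacy result is at risk. The change is a cheap improvement to subject safety that should be made; it does not correct an invalid analysis.

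**What to change.** Amend section 11.6, the Visit 4 description in section 5.0, and the Study Calendar as follows.

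- Add one scheduled phone or message contact by existing study staff a few days after the biopsy, on a day set by the study physician.
- Ask about infection, bleeding, bruising and pain.
- Record the answers in the CRF and refer any positive answer to the study physician.
- State that active enquiry ends at that contact and that later spontaneous reports, such as a scar, are still recorded.

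**Cost.** An amendment through the IRB, probably a consent form revision, and participation extended by a few days. Staff time is about 2.5 hours if 30 completers are each reached at the first attempt, and 12.5 hours if all 50 enrolled need three attempts, at the assumed 5 minutes per attempt. CRF entry and any referrals are extra. No new procedure or additional staff is needed.

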## **12.0 Ethical Considerations**

---

This study will be conducted in accordance with all applicable government regulations and University of Arkansas for Medical Sciences (UAMS) research policies and procedures. This protocol and any amendments will be submitted and approved by the UAMS Institutional Review Board (IRB) to conduct the study.

The formal consent of each subject, using the IRB-approved consent form, will be obtained before that subject is submitted to any study procedure. All subjects for this study will be provided a consent form describing this study and providing sufficient information in language suitable for subjects to make an informed decision about their participation in this study. The person obtaining consent will thoroughly explain each element of the document and outline the risks and benefits, alternate treatment(s), and requirements of the study. The consent process will take place in a quiet and private room, and subjects may take as much time as needed to make a decision about their participation. Participation privacy will be maintained and questions regarding participation will be answered. No coercion or undue influence will be used in the consent process. This consent form must be signed by the subject and the individual obtaining the consent. A copy of the signed consent will be given to the participant, and

the informed consent process will be documented in each subject's research record.

---

